11.1 TOXICITIES/SIDE EFFECTS

11.2 Rifaximin

The safety of Rifaximin for the treatment of infectious diarrhea was assessed in 2 placebo controlled trials. Discontinuation of the drug due to adverse reactions occurred in < 0.4% of patients. Those adverse reactions were taste loss, diarrhea, weight loss, anorexia, nausea and nasal passage irritation.

Side effects include: [25]

>10%:

- Cardiovascular: Peripheral edema (15%)
- Central nervous system: Dizziness (13%), fatigue (12%)
- Hepatic: Ascites (11%)
- Gastrointestinal:

Nausea (14%) 2% to 10%:

- Cardiovascular: Chest pain (>2% to 5%), hypotension (>2% to 5%)
- Central nervous system: Headache (10%), depression (7%), fever (6%), amnesia (>2% to 5%), attention disturbance (>2% to 5%), confusion (>2% to 5%), hypoesthesia (>2% to 5%), pain (>2% to 5%), tremor
- Dermatological: Pruritus (9%), rash (5%), cellulitis (>2% to 5%)
- Endocrine and metabolism: Hyper-/hypoglycemia (>2% to 5%), hyperkalemia (>2% to 5%), hyponatremia (>2% to 5%)
- Gastrointestinal: Abdominal pain (6% to 9%), anorexia (>2% to 5%), dehydration (>2% to 5%), esophageal varices (>2% to 5%), weight gain (>2% to 5%), xerostomia (>2% to 5%)
- Hematologic: Anemia (8%)
- Neuromuscular & skeletal: Muscle spasms (9%), arthralgia (6%), myalgia (>2% to 5%)
- Respiratory: Nasopharyngitis (7%), dyspnea (6%), epistaxis (>2% to 5%), pneumonia (>2% to 5%), rhinitis (>2% to 5%), upper respiratory tract infection (>2% to 5%)
- Miscellaneous: Influenza-like illness (>2% to 5%)

<2%, postmarketing, and/or case reports (limited to important or life-threatening):

Abnormal dreams, allergic dermatitis, anaphylaxis, angioneurotic edema (including tongue and facial edema with dysphagia), CDAD, dysuria, exfoliative dermatitis, flushing, hematuria, hypersensitivity reactions, insomnia, lymphocytosis, monocytosis, motion sickness, neutropenia, polyuria, proteinuria, sunburn, tinnitus, urticaria

Drug interactions: [25]

Although in vitro studies have suggested that rifaximin induces CYP3A4, no differences in midazolam (also induces CYP3A4) concentrations were found after administration of midazolam alone and midazolam and rifaximin together. Rifaximin had also been shown to have no effect on the oral contraceptive pill. No drug interactions have been reported to date.

11.3 Metronidazole

Memorial Sloan Kettering Cancer Center
[name]
[name]

The two most significant adverse reactions reported when taking metronidazole are convulsive seizures and peripheral neuropathy; these occur in <0.5% of patients and are nearly always associated with prolonged administration. The most commonly experienced side effect is nausea (12% of patients).

Other side effects include: (Taken from Lexi-Drugs online)

- Cardiovascular: Flattening of the T-wave, flushing, syncope
- Central nervous system: Aseptic meningitis, ataxia, confusion, coordination impaired, depression, dizziness, encephalopathy, fever, headache, insomnia, irritability, seizure, vertigo
- Dermatologic: Erythematous rash, pruritus, Stevens-Johnson syndrome, urticaria
- Endocrine & metabolic: Disulfiram-like reaction, dysmenorrhea
- Gastrointestinal: Nausea (~12%), anorexia, abdominal cramping, constipation, diarrhea, epigastric distress, furry tongue, glossitis, pancreatitis (rare), proctitis, stomatitis, unusual/metallic taste, vomiting, xerostomia
- Genitourinary: Cystitis, darkened urine (rare), dyspareunia, dysuria, incontinence, libido decreased, pelvic pressure, polyuria, vaginal dryness, vaginitis
- Hematologic: Neutropenia (reversible), thrombocytopenia (reversible, rare)
- Local: Thrombophlebitis
- Neuromuscular & skeletal: Dysarthria, peripheral neuropathy, weakness
- Ocular: Optic neuropathy
- Respiratory: Nasal congestion, pharyngitis, rhinitis, sinusitis, pharyngitis
- Miscellaneous: Flu-like syndrome, joint pains resembling serum sickness, moniliasis.

Drug interactions include: (Taken from Lexi-Drugs online)

- Alcohol (Ethyl): Metronidazole may enhance the adverse/toxic effect of Alcohol (Ethyl). A disulfiram-like reaction may occur.
- BCG: Antibiotics may diminish the therapeutic effect of BCG.
- Busulfan: Metronidazole may increase the serum concentration of Busulfan.
- Calcineurin Inhibitors: Metronidazole may decrease the metabolism of Calcineurin Inhibitors.
- Colchicine: CYP3A4 Inhibitors (Moderate) may increase the serum concentration of Colchicine. Management: Reduce colchicine dose as directed when using with a moderate CYP3A4 inhibitor, and increase monitoring for colchicine-related toxicity. Use extra caution in patients with impaired renal and/or hepatic function.

Memorial Sloan Kettering Cancer Center
[name]
[name]

- || CYP3A4 Substrates: CYP3A4 Inhibitors (Moderate) may decrease the metabolism of CYP3A4 Substrates.
- || Disulfiram: Metronidazole may enhance the adverse/toxic effect of Disulfiram.
- || Eplerenone: CYP3A4 Inhibitors (Moderate) may increase the serum concentration of Eplerenone. Management: A lower starting dose of eplerenone (25 mg once daily for adults) is recommended in patients with hypertension who are also taking drugs that are moderate inhibitors of CYP3A4.
- || Everolimus: CYP3A4 Inhibitors (Moderate) may increase the serum concentration of Everolimus. Management: Use of this combination is not recommended without close everolimus concentration monitoring/dose adjustments. For renal cell carcinoma, an initial everolimus dose reduction to 2.5 mg/day (adult dose) is recommended.
- || Fentanyl: CYP3A4 Inhibitors (Moderate) may increase the serum concentration of Fentanyl. Management: Monitor patients extra closely for several days following initiation of the combination, and fentanyl dosage reductions should be made as appropriate.
- || Halofantrine: CYP3A4 Inhibitors (Moderate) may increase the serum concentration of Halofantrine.
- || Mebendazole: May enhance the adverse/toxic effect of Metronidazole. Particularly the risk for Stevens-Johnson Syndrome or Toxic Epidermal Necrolysis may be increased.
- || Mycophenolate: Metronidazole may decrease the serum concentration of Mycophenolate. Specifically, metronidazole may decrease concentrations of the active metabolite of mycophenolate.
- || Phenobarbital: May decrease the serum concentration of Metronidazole.
- || Phenytoin: Metronidazole may increase the serum concentration of Phenytoin. Phenytoin may decrease the serum concentration of Metronidazole.
- || Pimecrolimus: CYP3A4 Inhibitors (Moderate) may decrease the metabolism of Pimecrolimus.
- || Ranolazine: CYP3A4 Inhibitors (Moderate) may increase the serum concentration of Ranolazine. Management: Limit the ranolazine adult dose to a maximum of 500 mg twice daily in patients concurrently receiving moderate CYP3A4 inhibitors (e.g., diltiazem, verapamil, erythromycin, etc.).
- || Salmeterol: CYP3A4 Inhibitors (Moderate) may increase the serum concentration of Salmeterol.
- || Saxagliptin: CYP3A4 Inhibitors (Moderate) may increase the serum concentration of Saxagliptin.
- || Tipranavir: Metronidazole may enhance the adverse/toxic effect of Tipranavir.
- || Tolvaptan: CYP3A4 Inhibitors (Moderate) may increase the serum concentration of Tolvaptan.

- Typhoid Vaccine: Antibiotics may diminish the therapeutic effect of Typhoid Vaccine. Only the live attenuated Ty21a strain is affected. Management: Vaccination with live attenuated typhoid vaccine (Ty21a) should be avoided in patients being treated with systemic antibacterial agents. Use of this vaccine should be postponed until at least 24 hours after cessation of antibacterial agents.

12.0 CRITERIA FOR THERAPEUTIC RESPONSE/OUTCOME ASSESSMENT

The ultimate response to treatment with antibiotics for ARS will be with the MSKCC bowel function instrument. This is an 18 point questionnaire which takes about 10 minutes to complete. It can be completed either in the outpatient setting or at home. This instrument has been validated in the assessment of bowel function following rectal cancer surgery over a 4 week period.[5] The BFI score will be calculated by the consenting physicians.

The purpose of the correlative studies is to assess if symptoms of ARS, indicated by a reduced MSKCC bowel function instrument score are associated with increased bacterial content in the gastro-intestinal tract or with a specific pattern of bacterial colonization. To this end bacterial content in the small intestine will be assessed using the breath test and bacterial content and colonization patterns will be assessed from fecal stool samples.

13.1 CRITERIA FOR REMOVAL FROM STUDY

A patient has the right to withdraw from the study at any time without prejudice to his/her future medical care by his/her physician at the institution

Criteria for removal for the study include:

- Patient discretion
- Significant noncompliance by the patient (<75% of drug dose taken)
- Development of an grade 3 or 4 adverse reaction to rifaximin
- Recurrence of their rectal cancer
- Should a treating physician deem it necessary in the best interest of the patient

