7.0 RECRUITMENT PLAN

Patients who have had an anterior resection for rectal cancer at MSKCC will be identified from a prospective database maintained by the Colorectal Surgery Service. These patients will be contacted by a letter inviting them to participate in a randomized study designed to evaluate the beneficial effects of rifaximin and placebo on bowel function. **Appendix 1.** We will ask patients to participate in the trial based on their own personal perception of their symptoms. Patients will be asked in the letter to contact [name] (PI) or [name] (Research Fellow) by email, telephone, or letter. Patients who have not responded to the letter after one month will be contacted by phone and invited to participate. **Appendix 4.** Every attempt will be made to recruit women and minorities to participate in this study. Participation is voluntary. Patients who are interested in participating will be scheduled for a research clinic visit with [name] or another of the consenting professionals. Consenting patients will be registered and randomized at the initial clinic visit. We hope to recruit 70 patients, 35 in each arm in an attempt to have at least 30 patients per arm for analysis allowing for patient dropout.

Patients will also be asked to volunteer to submit stool samples and breath tests. Those who agree will be tested for stool bacteria and SIBO at the relevant time points along with the MSKCC BFI. For those patients who do not agree to volunteer to supply stool samples and breath test, they will be tested using the MSKCC BFI alone at the relevant time periods. All patients will fill out the stool log/diary. We hope to recruit half of the patients in each arm to participate in the extra testing. We are not testing all patients with stool sampling and breath tests as we feel it will hamper accrual into the trial. Patients will be reimbursed with a \$100 gift card for each outpatient visit to cover transport costs for participating in this trial. Following completion of the phase III portion of the trial, patients will be contacted by phone and offered to participate in a follow up single arm study to assess the efficacy of metronidazole in the treatment of bowel dysfunction.

Memorial Sloan Kettering Cancer Center
[name]
[name]

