9.0 TREATMENT/INTERVENTION PLAN

The planned treatment during this trial will be the administration of the antibiotic rifaximin 400mg bid for 4 weeks or a placebo bid for 4 weeks to patients with bowel dysfunction. Both rifaximin and placebo will be prepared in identical capsules by the research pharmacist at MSKCC and distributed to the outpatient pharmacies. Following registration to the trial patients will be given a prescription for the trial, which they will be able to fill out at one of the MSKCC satellite center outpatient pharmacies. Patients will be instructed to take their treatment at the same time in the morning and the evening. Any missed doses will be recorded in the stool diary/log. Once treatment has been completed patients will be asked to mail back the treatment container along with any unused medication.

Once the trial has been completed and patients have been unblinded, patients may elect to be treated with Rifaximin if they so wish.

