14.0 BIOSTATISTICS

This is a blinded randomized control trial to compare the efficacy of a four week treatment with the rifaximin versus placebo in the management of Anterior Resection Syndrome (ARS) following Sphincter Preserving Surgery (SPS) for low rectal cancers. Patients will be randomized into 2 groups, one to receive rifaximin 400mg bid for 4 weeks and one group to receive a placebo bid for 4 weeks.

The primary endpoint is the change in the MSKCC bowel function index from baseline to 4 weeks after the start of therapy. At 4 weeks the patients will have been on therapy for 4 consecutive weeks. The MSKCC bowel function index has been validated to examine 4 week changes in the bowel function. [5] It consists of 18 items to which patients respond using a 5-point Likert scale, ranging from Always to Never. There is a summary score, and three subscales with good internal consistency (Frequency ($\alpha=0.75$), Dietary ($\alpha=0.78$), Urgency ($\alpha=0.79$)) and test-retest reliability (total score =0.84, Frequency=0.74, Dietary=0.62, Urgency=0.87). Each subscale is scored by summing up the responses to the items in the subscale. If there are missing items within a subscale, the mean of the completed subscale items will be substituted for the item when >50 percent of the items in the subscale is completed. A global score will be calculated by adding the subscale scores. An additional aggregate score (total score) will also be calculated with the subscales and the single items. A subscale will be considered missing if more than one-half of the items are missing. The global score will be considered missing if any of the subscales or single items were missing. The average total score (frequency, urgency, dietary, plus four single items) among the 129 MSKCC rectal patients following SPS used to develop the bowel function index was 63.7 with standard deviation of 11.6 and range of 35 – 83. Larger BFI scores indicate better function. In this study the main comparison of interest is to examine whether the change in global-BFI from baseline to 4 weeks after four weeks of rifaximin is different from the change from baseline to 4 weeks of placebo. The analysis will be done using an ANCOVA model, with baseline BFI and treatment indicator as covariates and 4 week BFI as the dependent variable.

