Based on clinical observation, we expect the difference in BFI between the two treatments to be fairly large. We would like to accrue 30 patients in each arm stratified by surgical procedure (hand sewn versus stapled anastomosis) for randomization to ensure the two arms are balanced, as surgical procedure is known to correlate with BFI.

Power calculations are based on the global score on the BFI. Based on [name] work when developing the BFI score in 129 MSKCC rectal cancer patients, the lowest mean BFI score was found among the hand sewn patients. The mean BFI score for these patients was 42 with a standard deviation of 8 and 51.6 with a standard deviation of 9 among patients with stapled anastomosis. In a current prospective study of 225 patients which is still maturing, we have found that at 6 months, the BFI discriminates between many clinical parameters with one of the most significant predictors being hand sewn vs stapled anastomosis (a surrogate for tumor level) (Mean 43.3, std 7 (n=36) vs Mean 49.4, std 8 (n=81). Based on these data, we anticipate that a difference of 6 points on the BFI is clinically and statistically meaningful.

For our power calculation, we set the type I error at 5%. We assume that the placebo arm will have no change in BFI from baseline to 4 weeks after the start of therapy. We also assume that the baseline for both treatment groups will be on a similar

magnitude. In line with the above average scores and standard deviations in [name] past and ongoing studies, we assume that the standard deviation of the differences to be 8 and the average BFI score at baseline to be 44. Using a two-sided, two sample t-test, we will have 80% power to detect a difference of differences from 0 in the placebo arm to 5.8 in the rifaximin arm with 30 patients in each arm. We expect to accrue the 60 patients for this study in 1 year, with a plan to recruit 35 in each arm to account for dropout.

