17.1 PROTECTION OF HUMAN SUBJECTS

Patient wellbeing will always take precedence in this trial however there will be minimal patient risk during this trial. Adverse drug reactions will be the most significant risk to patient health; however rifaximin carries minimal side effects. Should patients develop grade 3 or 4 toxicity to the antibiotic treatment, their treatment will be stopped and they will be removed from the study. The patient will be responsible for all costs related to treatments and complications of treatment except the antibiotic treatment, the placebo, breath testing and stool sampling which will be provided by MSKCC. Participation in this clinical trial is voluntary and at any stage patients may opt out to pursue any alternative treatment they wish. Once the trial is unblinded patients who received placebo during the trial may be treated with rifaximin if they so wish.

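### Low compliance and grade 3-4 reactions remove patients from the study, and Section 14 does not say whether removed patients are followed or analysed, so the primary ANCOVA is open to post-randomisation exclusions

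*Combined protocol and SAP*

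**What the plan says.** Section 13.1 gives criteria for leaving the study, not only for leaving treatment. Two of them arise after randomisation and can depend on the drug received: "Significant noncompliance by the patient (<75% of drug dose taken" and "Development of an grade 3 or 4 adverse reaction to rifaximin". Section 17.1 treats stopping drug and leaving the study as two steps and requires both. For patients with "grade 3 or 4 toxicity to the antibiotic treatment", it says "their treatment will be stopped and they will be removed from the study".

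Section 14.0 defines the primary endpoint as change in BFI from baseline to 4 weeks and gives the model: "The analysis will be done using an ANCOVA model, with baseline BFI and treatment indicator as covariates", with the 4-week BFI as the dependent variable. It has rules for missing items and subscales. It names no analysis population, has no rule for a wholly missing 4-week score, and does not mention patients removed under Section 13.1.

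Two places show that some randomised patients are expected not to be analysed. Section 14.0 sets 30 per arm "with a plan to recruit 35 in each arm to account for dropout", and Section 7.0 recruits 70 "in an attempt to have at least 30 patients per arm for analysis allowing for patient dropout".

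The nearest text the other way is in Sections 1.0 and 4.2, which say that all patients are assessed with the BFI once treatment has ended. Neither says whether that includes a patient already removed.

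**The concern.** Randomisation protects the comparison only if patients stay in it whatever happens to them afterwards. Taking too little drug and having a severe reaction are both post-randomisation events. If they are more frequent in one arm and affect patients who are doing worse or better than the rest, leaving those patients out biases the treatment effect. More rifaximin removals among patients doing badly would flatter rifaximin. More placebo removals among such patients would work against it. Equal removal, similarly related to outcome in both arms, leaves the mean difference unbiased.

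The choice is also left open. Section 9.0 has patients return the container and unused drug after treatment, and Section 10.1 sets the 4-week BFI at days 26-35. Noncompliance found at container return may therefore concern a patient whose primary-endpoint score is already on file. The plan does not say whether that score is used, so someone could decide after seeing it. With about 30 patients per arm, a few such decisions are visible in the result.

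Finally, the toxicity criterion refers to rifaximin in Section 13.1 and to the antibiotic in Section 17.1. Neither says how it applies to a blinded patient who may be on placebo.

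**Working it through.** **The plan's own figure.** Inputs from Section 14.0: difference 5.8, SD of change 8, 30 per arm, two-sided 5%.
- Standard error = 8 × √(2/30) = 2.066, and 5.8/2.066 = 2.808.
- Power = Φ(2.808 − 1.960) = Φ(0.848) = 80.2%. The exact t-test gives 78.8%.
- The stated 80% reproduces. Recruiting 35 for 30 allows 5/35 = 14.3% dropout. The sample size is not in question.

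**Expected removals.** The documents give no noncompliance rate. Their only discontinuation rate for adverse reactions is below 0.4% (Section 11.2, infectious diarrhoea trials): 0.004 × 35 = 0.14 patients per arm. The toxicity route is probably rare. The compliance route cannot be quantified.

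**Illustration of bias.** Assumptions not in the documents: 35 per arm, no true effect, SD 8 at baseline and at 4 weeks with correlation 0.5, and removal of patients low on a score correlated 0.5 with BFI change.
- SD of change = 8 × √(2 × (1 − 0.5)) = 8, as in the plan.
- ANCOVA residual SD = 8 × √(1 − 0.25) = 6.93. Correlation of change with that residual = 6.93/8 = 0.866.
- Covariance of removal score and residual = 0.5 × 0.866 × 6.93 = 3.0.
- Removing the lowest k of 35 raises that arm's adjusted mean by about 3.0 × φ(c)/(1 − k/35), where c = Φ⁻¹(k/35).
- k = 1: 3.0 × 0.0653/0.9714 = 0.20. k = 3: 3.0 × 0.1566/0.9143 = 0.51. k = 5: 3.0 × 0.2256/0.8571 = 0.79.
- Type I error ≈ Φ(−1.96 + b/SE) + Φ(−1.96 − b/SE), where b is the bias and SE = 6.93 × √(1/n₁ + 1/n₂) for the patients kept.

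| Removed, rifaximin vs placebo | Bias, points | SE | Type I error, formula | Type I error, simulated |
|---|---|---|---|---|
| 1 vs 0 | 0.20 | 1.67 | 5.2% | 5.1-5.2% |
| 3 vs 1 | 0.51 − 0.20 = 0.31 | 1.71 | 5.4% | 5.3-5.7% |
| 5 vs 0 | 0.79 | 1.72 | 7.4% | 7.0-7.4% |

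The simulated ranges cover two removal rules: exactly the k lowest patients in each sample, or everyone below a fixed threshold with the same expected count. Simulated bias for 5 vs 0 is 0.77 to 0.80, and 0.77/5.8 = 13% of the planned difference.

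**Cost of analysing as randomised.** Suppose all 35 per arm contribute a score and k rifaximin patients gain nothing. The effect is 5.8 × (35 − k)/35. The t-test column uses SD 8 and the ANCOVA column uses residual SD 6.93.

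| k | Effect | Power, plan's t-test | Power, ANCOVA |
|---|---|---|---|
| 0 | 5.80 | 85% | 93% |
| 1 | 5.63 | 83% | 92% |
| 2 | 5.47 | 80% | 90% |
| 5 | 4.97 | 73% | 84% |

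For comparison, 30 completers per arm at 5.8 points have 79% (t-test) or 89% (ANCOVA). Adding the variance from mixing patients with and without benefit lowers the t-test figures to 82.5%, 79.9% and 71.3% for k = 1, 2 and 5.

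**The case against.** The best defence has three parts.

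First, Sections 1.0 and 4.2 say that all patients complete the BFI after treatment, and read plainly this could include those who stop early. This has force, but it does not settle the matter. It concerns assessment and not analysis, it does not mention removed patients, and removal from the study in Sections 13.1 and 17.1 points the other way.

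Second, the trial is double blind. Capsules are identical (Sections 4.3 and 9.0), and only dispensing pharmacists can see assignments (Section 15.3). That limits removals made knowing the arm. It does not prevent the drug itself from causing unequal compliance or toxicity, nor a choice about scores made after unblinding.

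Third, the illustrated harm is small. Modest imbalance barely moves the type I error, and reaching about 7% needs five removals in one arm, none in the other, and a removal-outcome correlation of 0.5. This stands in full and limits how much weight the point can carry.

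A reader might go further and infer that the plan discards removed patients' data or intends a per-protocol primary analysis. The documents do not support that. The allowance of 35 for 30 implies only that patients without a 4-week score fall out. No section says that a score already obtained is dropped, and none says that it is kept.

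**Conclusion.** The point holds as a gap that should be fixed. Sections 13.1 and 17.1 take patients out of the study for events that follow randomisation, and Section 14.0 does not say whether they are followed or analysed. The primary ANCOVA is therefore open to exclusions that may differ by arm and relate to outcome.

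Confidence is high about the silence and low about the size. On the illustrative assumptions, bias runs from about 0.2 points (1 vs 0) to 0.8 points (5 vs 0), and type I error from about 5.1% to 7.4%. The removal counts and the correlation are assumed. The sign reverses if the imbalance does, so a reader should not infer that the result must favour rifaximin. Likely harm is small unless removals are imbalanced. The firmer reason to act is that the use of these scores should not be left to a decision made after they are seen.

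**What to change.** - **Sections 13.1 and 17.1:** state that patients who meet the compliance or toxicity criterion stay in follow-up for the 4- and 8-week BFI unless they withdraw consent. Section 10.1 already allows completion at home by mail or email. No rule on stopping drug changes.
- **Section 14.0:** state that the primary ANCOVA analyses patients in their assigned arm, using every 4-week BFI obtained regardless of compliance or removal. Report patients who took at least 75% of the dose as a sensitivity analysis only. "Any missed doses will be recorded in the stool diary/log" (Section 9.0), so the compliance data for this are already collected.
- **Toxicity wording:** Sections 13.1 and 17.1 must be reconciled so that the criterion can be read for both blinded arms.

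The cost is a wording amendment and a few more home questionnaires. The statistical downside is a possibly smaller as-randomised effect: if two rifaximin patients gain nothing, power with 35 per arm is about 80% on the plan's t-test or 90% under the assumed ANCOVA. Five such patients would bring it to 73% or 84%.
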